#### 8.5 **Quality complaints**

In case of quality complaints (technical or transportation claims), the Investigator must report to the Sponsor thereon within 24 hours after receipt of information as described in Appendix 2. Any AE associated with the quality complaints shall be documented and reported as described in Sections 8.3.4 and 8.3.5.

# 8.6 Special cases

Special cases may be serious or non-serious (see below) and must be reported as AEs pursuant to Sections 8.3.4 and 8.3.5 even in absence of other AEs associated with the special cases.

A special case scenario	The Investigator must inform LPPV
Exposure during breastfeeding	X
Intentional overdose by the patient (including the suicide attempts which are always considered to be serious)	Only if associated with SAE
Drug interactions	Only if associated with SAE
Withdrawal response/syndrome	Only if associated with SAE
Drug dependency, misuse, abuse, or addiction (always serious)	Х
Suspected transmission of infectious agents (always serious)	Х
Death (always serious even without other events)	Х

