#### 6.3 Methods to monitor the subjects' compliance with trial procedures

At every visit after Visit 1, the subjects' compliance will be checked by counting the unused drug and analysis of the patient's diaries. It should be noted that the drugs doses stipulated by the protocol are 6 to 10 (maximum) lozenges per day (Angal),

and to 6 lozenges per day with at least 2-hour interval (ANTI-ANGIN® FORMULA). The both drugs should be taken when needed (a sore throat).

In view of the nature of drug intake (when needed), the lower margin of compliance will not be evaluated; the number of used lozenges is compared to maximum amounts stated in the protocol for the study drug (up to 10 lozenges per day for Angal) or Prescribing Information for the comparator drug (up to 6 lozenges per day for ANTI-ANGIN® FORMULA).

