# **8.3** Requirements for reporting, registration, and reporting of AEs and intercurrent diseases

# 8.3.1 Definitions of adverse events and serious adverse events

Adverse event (AE) is any adverse medical event identified in a patient or a clinical trial patient after the use of the drug, which may or may not have a causal relationship with its usage. Thus, adverse event (AE) can represent any adverse symptom (including laboratory deviation from the norm), complaint, or disease, for which a temporal causal relation cannot be excluded with the use of medicinal (study) product, regardless of the presence or absence of such a relation.

Serious adverse event (SAE) represents any event, unfavorable from medical perspective, which with any dose:

- Resulted in death;
- Is life threatening;
- Results in disability/incapacity to work;
- Is a congenital anomaly or development defect;
- Requires hospitalization or its extension;
- Is significant from medical perspective: a decision whether expedited reports is feasible in other situations (e.g., in case of events important from medical perspective, which are not directly life-threatening for a

patient, do not result in death or hospitalization, but pose the patient to risk or require intervention to prevent one of the above outcomes) shall be made on the basis of medical and scientific evaluation. Such cases should be usually considered serious adverse events.

Adverse drug reaction (ADR) is any adverse event which might have causal relation to the drug in the opinion of the Investigator or Sponsor (see Section 8.3.3 below).

An unexpected adverse reaction is defined as an adverse drug reaction, the nature or severity of which is not consistent with the Reference Safety Information (e.g. SmPC, Investigator's Brochure). The term "severity" is used to describe the intensity of a specific event. This term should be distinguished from the term "serious". Reports which add significant information on specificity, increase in incidence, or severity of the known, already documented serious adverse reactions, constitute the unforeseen events.

Information about side effects already known for this study drug is available in the Investigator's Brochure. This information will be included into Patient Information Sheet, and it should be discussed with the trial subjects.

More details are given in Brief Reference Manual for filling in the Serious Adverse Event Report Form (to be provided by the Sponsor).

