# 9.1.4 Safety parameters analysis

A descriptive part of the safety analysis will include an evaluation of incidences and two-sided CI 95% for the following parameters in every trial group:

- AEs: the incidence in total and for separate categories (according to MedDRA), for the trial and by groups;
- SAEs: the incidence in total and for separate categories (according to MedDRA), for the trial and by groups;
- Incidence of clinically significant changes of the physical examination results by visits and groups;
- Incidence of clinically significant changes of the laboratory results by visits and groups;
- Incidence of clinically significant changes of the vital signs (body temperature, BP, pulse rate, HR) by visits and groups;
- Incidence of clinically significant changes of the ECG parameters by visits and groups;
- Global tolerance evaluation during the trial by the Investigator and patient;

The Fisher's exact test will be used to compare incidences between the groups, and chi-square will be used to compare the global therapy tolerability by the Investigator and patient. The McNemar's test will be used to evaluate for the dynamic changes during the trial (before–after) for all the repeatedly evaluated incidences in every group.

In addition to the incidence, all the quantitative safety parameters will be presented in a table form (laboratory data, vital signs, ECG) by visits and groups. The difference will be evaluated using 2-way-ANOVA (group and visit numbers will serve as the relevant factors). The post-hoc criteria will be used in case of significant difference.

Safety analysis will be performed on the safety population.

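### Section 8.6 makes special cases reportable as AEs even without a medical event, and the between-arm AE/SAE comparison does not separate them, so harm-free overuse may be counted, possibly unequally between arms

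*Protocol*

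**What the plan says.** Protocol 8.6 states that special cases "must be reported as AEs pursuant to Sections 8.3.4 and 8.3.5 even in absence of other AEs associated with the special cases". Its table lists the scenarios. One row is "Drug dependency, misuse, abuse, or addiction (always serious". A separate row is "Intentional overdose by the patient (including the suicide attempts which are always considered to be serious". Neither misuse nor overdose is defined by a number of lozenges.

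Protocol 8.3.1 defines an AE as an adverse medical event. For seriousness it says "Serious adverse event (SAE) represents any event, unfavorable from medical perspective, which with any dose" leads to one of the listed outcomes or is judged medically significant. Misuse is not on that list.

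Protocol 9.1.4 includes among the incidences to be reported "SAEs: the incidence in total and for separate categories (according to MedDRA), for the trial and by groups", has a matching item for AEs, and compares incidences between groups with Fisher's exact test. SAP 4.1.4 compares AE incidence between arms with Pearson's chi-squared test.

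Protocol 6.3 sets no lower limit on compliance. Instead, "the number of used lozenges is compared to maximum amounts stated in the protocol for the study drug", given as "up to 10 lozenges per day for Angal", or to the comparator's prescribing information, given as "up to 6 lozenges per day for ANTI-ANGIN".

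**The concern.** A rule written for safety notification feeds an analysis that is meant to count medical events. Nothing in 9.1.4, in SAP 4.1.4 or among the SAP's 24 table templates removes or separates a special case in which nothing happened to the patient.

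The act most likely to raise the question is taking too many lozenges, and its threshold differs by arm: 7 to 10 lozenges in a day is within the Angal ceiling and above the comparator ceiling. The trial is open-label (Protocol 4.3.2), so whoever decides between non-compliance, overdose and misuse knows the arm. Identical behaviour could therefore produce an AE, or even an SAE, in one arm and no report in the other.

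At stake is the AE comparison, a stated secondary goal (Protocol 3.2). AE and SAE rates are also the first safety parameter listed in Protocol 8.1.

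**Working it through.** **1. The route into the tables.** 8.6 sends special cases to 8.3.4 and 8.3.5. 8.3.4 puts every AE, serious or not, on the AE pages of the case record form. 9.1.4 and SAP 4.1.4 count what is recorded as an AE. SAP Tables 21 and 22 split events by description, severity and seriousness only. No step asks whether a medical event occurred.

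**2. How use above the daily ceiling could be classified.**

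| Reading | Source | Counted as AE? | Automatically serious? |
|---|---|---|---|
| Non-compliance | Protocol 5.3.1 item 8; 6.3 | No | No |
| Intentional overdose | Protocol 8.6 | Yes | Only suicide attempts |
| Misuse | Protocol 8.6 | Yes | Yes |

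The protocol does not choose between these readings. The overdose text in 2.1.1 speaks of major misuse of the prescribing information, so the third reading is possible but not established.

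**3. Which arm would be affected.** The inputs are the ceilings (6.3), the 2-hour minimum interval and treatment durations (4.4.4), the packs (4.4.2) and the quantities dispensed (4.4.3).

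- Daily use: 10 lozenges at 2-hour intervals span 9 × 2 = 18 h; 6 span 5 × 2 = 10 h. An assumed 16-hour waking day fits 16/2 + 1 = 9, which is above 6 and below 10. This points to the comparator arm.
- Course totals: Angal 2 × 24 = 48 dispensed against 10 × 4 = 40, leaving 8 spare. Comparator 3 × 10 = 30 dispensed against 6 × 5 = 30, leaving none. This points to the Angal arm. (The remark in 4.4.3 that an excess is supplied fits Angal only; that section and the ceilings should be reconciled.)
- Single days: after three days at the ceiling, 48 − 30 = 18 Angal and 30 − 18 = 12 comparator lozenges remain, so both arms can exceed the ceiling on one day.

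The documents give no usage data, so the direction stays open.

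**4. How many reports would matter.** Take 140 per arm (Protocol synopsis) and k extra reports, all in one arm.

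With no other events, two-sided Fisher p = 2·C(140,k)/C(280,k):

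- k = 5: 0.060
- k = 6: 0.030
- k = 7: 0.0145

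Uncorrected Pearson chi-squared = 280k/(280 − k), against a critical value of 3.84:

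- k = 3: 840/277 = 3.03
- k = 4: 1120/276 = 4.06 (p = 0.044)

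With equal background events in both arms, the smallest k giving p < 0.05 was found by enumerating the 2 × 2 tables:

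| Other events per arm (assumption) | Fisher | Chi-squared |
|---|---|---|
| 0 | 6 (4.3%) | 4 (2.9%) |
| 5% (7 of 140) | 11 (7.9%) | 10 (7.1%) |
| 10% (14 of 140) | 13 (9.3%) | 12 (8.6%) |

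The first row is the relevant one for SAEs if their background is near zero. That is an assumption, though Protocol 2.2.2 says that no SAEs were reported for the study drug. For scale, assumed report rates of 2%, 5% and 10% in one arm give 140 × 0.02 = 2.8, 140 × 0.05 = 7 and 140 × 0.10 = 14 reports.

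**The case against.** The strongest reply is that overuse need not reach the AE tables at all. It can be handled as non-compliance. If it is a special case, the overdose row is at least as natural as the misuse row, which sits with dependency, abuse and addiction; in the overdose row only suicide attempts are always serious. Even overdose is doubtful for a few extra lozenges, because 2.1.1 illustrates excessive Angal use with more than 20 a day. This stands: nothing in the protocol makes 7 lozenges an automatic SAE.

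A reader might infer from the ceilings of 6 and 10 that the excess would fall mainly in the comparator arm and bias the safety comparison in favour of Angal. The documents do not support that. There are no usage data, and the pack sizes point the other way for course totals.

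A reader might also see a contradiction inside 8.6, because the text requires all special cases to be reported while the table limits notice of overdose to the local pharmacovigilance person to cases with an SAE. The two can coexist: 8.3.4 governs recording in the case record form and 8.3.5 governs SAE notification.

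It can also be said that 8.6 deliberately extends 8.3.1, that 8.3.1 itself admits medically significant events by judgement, and that event descriptions in SAP Tables 21 to 23 would let a reader spot such cases. All true, but the totals and the between-arm tests would still include them.

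**Conclusion.** The point holds as a gap between a recording rule and an analysis rule. An explicit instruction places reports outside the 8.3.1 AE definition into a between-arm comparison, and neither document separates them. With different daily ceilings and open-label classification, the contribution may be unequal between arms.

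Its direction and size are not established. The 6 v 0 and 4 v 0 results are worst cases: they need every report in one arm and no background events and, for SAEs, every case filed as misuse. With an assumed background of 5% or 10%, 10 to 13 one-sided reports are needed. It would be wrong to conclude that the plan inflates comparator SAEs.

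The primary non-inferiority result is unaffected. SAP Section 4 rests the non-inferiority conclusion on the primary parameter alone and treats safety variables as of research interest. The clarification is still worth making before analysis, because the AE comparison is a stated goal and the change is cheap.

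**What to change.** Keep the recording and notification duties of 8.6, and leave seriousness as recorded, so that the matching of the clinical and safety databases in Protocol 8.7 is not disturbed. Then:

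- In Protocol 9.1.4 and SAP 4.1.4, base the between-arm AE comparison, and the SAE comparison in 9.1.4, on events that meet 8.3.1.
- List special cases without an associated medical event separately by arm, and show AE and SAE totals with and without them.
- State before analysis, identically for both arms, how use above the daily ceiling is classified: non-compliance, overdose or misuse. Reconcile 6.3, 8.3.1 and 8.6 accordingly. Which classification is right is for the sponsor to decide.

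The cost is wording in these sections and one extra listing. The small downside is that the headline AE rate no longer contains harm-free special cases and must be read together with the listing.

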### 8.7 Information verification

Verification of information between a safety database of the Sponsor and a clinical database stored in CRO will be performed at the end of the trial according to a verification plan by comparison of the relevant summary tables from the both databases.

During data processing, eCRF/information in the clinical database will be reviewed for potentially unreported SAEs. Any potential SAE requires an exact match in the following parameters between the clinical database and safety database: trial number, center number, subject number, randomization number, study drug, degree of severity, date of death (if applicable), and causality according to the Investigator's evaluation. All other parameters must be credible and consistent from medical perspective. A thorough verification of information must be performed for every event subject to reporting as well as any other events of special interest (if applicable) considered to be related to the study drug, including dates of the drug use, outcome, medical history, and concomitant therapy.

# 9 Statistics

# 9.1 Description of the statistical methods to be used including the terms for every planned interim analysis

Statistical analysis will be performed using R Project specialized software.

The continuous (quantitative) data will be presented as a number of observations, arithmetic mean, confidence interval (CI) 95% for the mean (unless stated otherwise), standard deviation (SD), median, interquartile range (IQR), minimum, and maximum.

The serial, categorical, and qualitative data will be presented as absolute incidences (number of observations), relative incidences (%), and CI 95% (unless otherwise stated).

The concomitant diseases and AEs will be coded using MedDRA terms.

This section contains a brief description of the planned analysis. Full analysis will be presented in the statistical analysis plan.

### 9.1.1 Demographic and other baseline data (group comparability for the analysis)

All the data obtained in the groups before the trial therapy initiation (demographic, laboratory, instrumental, and physical examinations data, vital signs, etc.) will be compared between the groups to determine the groups' comparability for analysis.

The Fisher's exact test and chi-square will be used to compare the qualitative and serial data, while the t-test or the Mann–Whitney test will be used for the quantitative data (depending on the quantitative data distribution).

### 9.1.2. Analysis of the primary efficacy endpoint

The primary outcome measure in this trial was the proportion of patients without sore throat after 3 days of therapy, on Day 4, as evaluated by the Investigator according to the Tonsillopharyngitis Severity Score (TSS), in both Angal and ANTI-ANGIN® FORMULA arms.

A null hypothesis of this trial assumes that Angal, the study drug, is less effective than ANTI-ANGIN® FORMULA, the comparator drug. An alternative hypothesis of this trial assumes that Angal, the study drug, is not less effective than ANTI-ANGIN® FORMULA, the comparator drug.

14.5% is chosen as a non-inferiority margin (see Section 9.2 for a justification) based on the results of a randomized, placebo-controlled trial of a similar drug.

The group comparison will be carried out using the Fisher's exact test (one-sided test, in connection with the null hypothesis of non-inferiority).

For the proportion difference, the 90% confidence interval (CI) will be calculated according to the procedure described in Newcombe, Robert G. "Interval Estimation for the Difference Between Independent Proportions: Comparison of Eleven Methods," Statistics in Medicine, 17, 873-890 (1998).

Thus, the non-inferiority will be confirmed if the limit of the two-sided 90% confidence interval for the difference in the proportions will be 14.5% or lower.

A primary endpoint analysis will be conducted both for the ITT (main analysis) and PP populations (additional analysis).

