# Confidence Intervals of Difference (P1-P2)

Interval	Estimated	Confidence	Confidence
Method	Value	Limit	Limit
Chi-Square	0.2561	0.1456	0.3666

(Pearson)

(The calculation results are presented in the language of the original source)

In view of the considered nosology and absence of significant factors requiring a conservative approach for determination of the non-inferiority margin, for this purpose we can use a two-sided CI 90%. In such a case, the lower limit for the rate difference (a two-sided CI 95%) will amount to 14.6%. Therefore, a margin of 14.5% is considered to be justified.

Based on the above, we may hypothetically expect a rate of positive response to a new

	therapy (absence of a sore throat as an efficacy measure) at least 63%. A statistic hypothesis tested:		
	H0: $p_1-p_2 \le -14.5\%$ compared to H1: $p_1-p_2 > -14.5\%$ If a null hypothesis is rejected, a conclusion will be made that efficacy of the study drug is not less than that of the comparator drug.		
	A sample size is evaluated based on the following assumptions:		
	- A rate of positive response to therapy (absence of a sore throat as an efficacy measure) in a comparator drug arm is 63%.		
	- A rate of positive response to therapy (absence of a sore throat as an efficacy measure) in a study drug arm is 65% (chosen within the tested hypothesis and based on the sample size and expected positive response).		
	- Power = 80%		
	- A non-inferiority margin: 14.5		
	- Significance level: 97.5%		
	- Randomization in 1:1 ratio (study drug : comparator drug). A number of patients required at 80% power and 2.5% one-sided significance level to prove the hypothesis of the study drug efficacy not more than 14.5% inferior to that of the comparator drug (determined by absence of a sore throat after 3 days of therapy) if 128 patients in every arm.		
Interim analysis	An interim analysis may be conducted after receipt of efficacy data for Angal and ANTI-ANGIN ® FORMULA, spray, after 3 days of therapy, on Day 4, for 100 patients in every arm. The interim analysis includes demographic data, data on the anamnesis and concomitant therapy, available data on efficacy and safety of Angal and ANTI-ANGIN ® FORMULA drugs.		
Blinding, randomization	This trial will be open, without blinding. The patients will be included by randomization in 1:1 ratio using envelopes at the trial site.		

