### 9.3 Applicable significance level

All statistical analyses in this trial will be conducted at 95% significance level (a threshold p value for confirmation of statistical significance is below 0.05), except for the primary endpoint where an one-sided statistical criterion will be used with 97.5% significance level (a threshold p value is below 0.025). The two-sided statistical criteria will be used for all other parameters.

For the primary endpoint evaluation, 90% CI will be calculated for the proportions difference with further evaluation of its lower boundary limit.

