## 3.9 Null and alternative trial hypotheses

Based on the trial objectives, the following hypotheses were drawn for testing:

Null hypothesis (H0): Difference in the primary endpoint achievement incidence while using Angal, the study drug, and ANTI-ANGIN® FORMULA, the original drug, for treatment of acute infectious and inflammatory pharyngeal diseases will exceed 14.5% in favor of ANTI-ANGIN® FORMULA:

$$H_0: p_1 - p_2 \le -0.145$$

Alternative hypothesis ( $H_A$ ): Difference in the primary endpoint achievement incidence while using Angal, the study drug, and ANTI-ANGIN® FORMULA, the original drug, for treatment of acute infectious and inflammatory pharyngeal diseases will not exceed 14.5% in favor of ANTI-ANGIN® FORMULA:

$$H_A: P_1 - P_2 > -0.145$$

Where p1 and p2 is the primary endpoint achievement incidence while using Angal, the study drug, and ANTI-ANGIN® FORMULA, the original drug, respectively.

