## 3.10 Significance level

All statistical analyses in this trial will be conducted at 95% significance level (a threshold p value for confirmation of statistical significance is below 0.05), except for the primary endpoint where a one-sided statistical criterion will be used with 95% significance level (a threshold p value is below 0.05). The two-sided statistical criteria will be used for all other parameters.

For the primary endpoint evaluation, 90% CI will be calculated for the proportions difference with further evaluation of its lower boundary limit.

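### The one-sided Fisher's exact test named for the primary endpoint ignores the 14.5-point margin, and its role beside the confidence interval rule is not stated

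*Protocol*

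**What the plan says.** Protocol 9.1.2 and SAP 4.1.2 carry the same sentence on the primary comparison: "The group comparison will be carried out using the Fisher's exact test (one-sided test, in connection with the null hypothesis of non-inferiority". Each then plans a two-sided 90% Newcombe interval for the difference in proportions. Each confirms non-inferiority if the limit of that interval is 14.5% or lower, without saying which limit or which sign. SAP 4 also bases confirmation on the 90% interval and its lower limit, and does not mention Fisher's test.

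The formal hypotheses contain the margin. Protocol 9.2 and SAP 3.9 set H0: p1 − p2 ≤ −0.145, with p1 for Angal; in SAP 3.9 the null is that the difference for "acute infectious and inflammatory pharyngeal diseases will exceed 14.5% in favor of" the comparator. Section 9.1.2 itself words the pair without the margin ("An alternative hypothesis of this trial assumes that Angal, the study drug, is not less effective than" the comparator), although its next paragraph says "14.5% is chosen as a non-inferiority margin (see Section 9.2 for a justification". In the synopsis, rejecting the margin null means that "a conclusion will be made that efficacy of the study drug is not less than that of the comparator drug".

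On thresholds, Protocol 9.3 has a "one-sided statistical criterion will be used with 97.5% significance level (a threshold p value is below 0.025", and SAP 3.10 has a "one-sided statistical criterion will be used with 95% significance level (a threshold p value is below 0.05". Both sections then turn to the lower limit of the 90% interval.

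**The concern.** The sentence ties the test to the non-inferiority null, but Fisher's exact test conditions on the table margins under p1 = p2. The 14.5 points appear nowhere in its calculation. In the Angal-better direction it is a superiority test. Neither document describes a margin-shifted version.

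Fisher's is also the only test named for the primary endpoint, and both documents attach a one-sided p-value threshold to that endpoint. A report that follows the text would print a primary p-value, described as a non-inferiority test, that usually misses its threshold when the drug performs as planned. The interval next to it would usually succeed. The role of the p-value would then have to be settled after the results are known.

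**Working it through.** **Inputs.** Angal 65%, comparator 63%, margin 14.5 points, 128 evaluable and 140 randomized per arm (Protocol 9.2); one-sided thresholds 0.025 (Protocol 9.3) and 0.05 (SAP 3.10); two-sided 90% Newcombe interval (Protocol 9.1.2, SAP 4.1.2).

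**The plan's own figure.** Standard error at 128 per arm = √[(0.65×0.35 + 0.63×0.37)/128] = √(0.4606/128) = 0.0600. Power at one-sided 2.5% = Φ[(0.02 + 0.145)/0.0600 − 1.96] = Φ(0.79) = 78.5%. Exact enumeration with a 95% Newcombe interval gives 79.2%. Both are close to the stated 80%. The closed form gives n = 0.4606 × [(1.960 + 0.842)/0.165]² ≈ 133 rather than 128; the protocol's program check used 1000 simulations, which may explain the gap. So 128 per arm is sized for a margin-based criterion, not for Fisher's test.

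**Method.** All pairs (x1, x2) of responder counts were enumerated and weighted by their binomial probabilities. For each pair:
- Fisher, Angal better: p = P(X ≥ x1), with X hypergeometric given x1 + x2 responders in total.
- Interval: L = d − √[(p̂1 − l1)² + (u2 − p̂2)²], where d = p̂1 − p̂2, and l1 and u2 are the Wilson limits at z = 1.645. Success is L > −0.145.

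**One example near the planning rates.** With 83/128 v 81/128, d = 0.0156, l1 = 0.5766 and u2 = 0.6995. Then L = 0.0156 − √(0.0718² + 0.0667²) = −0.082. This is above −0.145, so the interval shows non-inferiority. Fisher's one-sided p is 0.448.

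**What Fisher's test requires.** With 81/128 on the comparator, p < 0.025 needs 97/128 on Angal, that is (97 − 81)/128 = 12.5 points better (p = 0.021; 96/128 gives 0.029). For p < 0.05 it needs 95/128, or 10.9 points better.

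**Probabilities over all outcomes.**

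| True rates, n per arm | Fisher p < 0.025 | Fisher p < 0.05 | 90% CI lower limit > −14.5 points |
|---|---|---|---|
| 65% v 63%, 128 | 3.9% | 7.7% | 87.4% |
| 65% v 63%, 140 | 4.3% | 7.7% | 89.9% |
| 63% v 63%, 128 | 1.8% | 4.0% | 78.5% |
| 60% v 63%, 128 | 0.5% | 1.3% | 60.5% |

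At the planning rates Fisher's p is therefore non-significant in 100 − 3.9 = 96.1% (protocol threshold) or 100 − 7.7 = 92.3% (SAP threshold).

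**Disagreement.** At 128 and at 140 per arm, no outcome has Fisher p < 0.05 with a failed interval. The probability that the interval succeeds while Fisher misses is then a simple difference: 87.4 − 3.9 = 83.5% at 0.025, and 87.4 − 7.7 = 79.7% at 0.05.

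**The interval wording.** Taken literally on the lower limit, a limit at or below +14.5% occurs in practically every trial, including when the true rates are 48.5% v 63%, a deficit equal to the margin. Read as L > −0.145, the rule passes 4.9% of trials at those rates, which is what a one-sided 5% rule should do.

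**The case against.** The strongest reply is that the interval decides. No sentence makes a significant Fisher p a condition for non-inferiority. The only confirmation rule in Protocol 9.1.2, SAP 4 and SAP 4.1.2 is the 90% interval. This stands, and it rules out three stronger readings.

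- A reader might take 96% as the chance that a truly non-inferior Angal fails the trial. It is the miss rate of one p-value, at the protocol threshold and the planning rates. At the SAP threshold it is 92%, and other true rates inside the margin give other figures.
- A reader might infer two co-primary criteria, one of which must be dropped. The text describes a group comparison and then a confirmation rule, and the remark in parentheses may only explain why the test is one-sided. The thresholds need not belong to Fisher's test alone: both sections speak of a one-sided criterion and go straight on to the interval, and 0.05 in SAP 3.10 is exactly the level of a 90% limit. What is missing is any statement of the p-value's role.
- A reader might fear that the test will be pointed at inferiority and a non-significant result taken as support. Nothing in either document plans that. In the Angal-better direction Fisher's test adds no false claim, because it is never significant where the interval fails.

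The margin-free hypothesis wording is also softened by its surroundings: the margin follows at once in 9.1.2, and the margin hypotheses precede the synopsis conclusion.

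The reply does not excuse linking the test to a null that it cannot test. Nor is the interval rule a safe fallback while it names neither limit nor sign.

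**Conclusion.** The point holds as a mis-specified test with an undefined role. It does not show that the trial would fail 96% of the time. The named test does not address the primary hypothesis, and with the planned effect it would contradict the interval in about 80% (SAP threshold) to 83% (protocol threshold) of trials.

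The figures assume that the test is pointed at Angal being better, which the documents do not state; that the Newcombe interval is the hybrid score form without continuity correction, since the cited paper compares eleven methods and neither document picks one; and that the interval rule means a lower limit above −14.5 points. The protocol's 0.025 also conflicts with the one-sided 5% level of a 90% interval. That is a separate matter, but the level has to be settled before any replacement test can be specified.

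**What to change.** - In Protocol 9.1.2 and SAP 4.1.2, delete the Fisher sentence. Alternatively, replace it with a score test of H0: p1 − p2 ≤ −0.145 (Farrington-Manning or Miettinen-Nurminen) at the same one-sided level as the interval.
- Label any Fisher p-value that is kept as a superiority test with no part in the non-inferiority conclusion.
- In the same two sections, replace the 14.5% wording of the interval rule with: *lower limit of the CI for p1 − p2 (Angal minus comparator) greater than −14.5 percentage points*. Without this, letting the interval decide alone does not work.
- Use the 9.2 hypotheses in 9.1.2, and end the synopsis conclusion with: *not lower by more than 14.5 percentage points*.

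The cost is a few sentences in the protocol and SAP. No data collection, visit or patient is affected, and the sample size stays as it is.
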